**Plans for Assuring Data Accuracy and Protocol Compliance**

All study data for AMC clinical trials are entered directly by AMC clinical site staff into the applicable clinical data entry system for the trial. During data entry, the system performs validation checks on many fields and performs consistency checks between select fields. Range checks are placed on each field to eliminate entry of out-of-range values. Edit check programs are run on the database on a set schedule to identify and resolve inconsistencies between forms or data collected at different points in time. Submitted data entry forms are reviewed for compliance with the protocol and data entry instructions according to the AMC ODMC's standards for data quality processes. AMC ODMC staff routinely interacts with site staff to resolve any data submission problems.

In accordance with NCI guidelines, the AMC ODMC conducts audits at the AMC sites to evaluate compliance with regulatory issues, and to review data for specific cases by checking source documents. These reports are sent to the site principal investigator and to the NCI. In the event that major violations are identified, sites are asked to provide a written corrective and preventative action plan to correct deficiencies. If needed, a repeat site audit is conducted. In the event that a site does not correct deficiencies in a pre-determined time frame, the AMC Executive Committee has the option to implement remedial action(s) for the site. Possible actions include, but are not limited to, suspending enrollment of new patients to AMC trials until deficiencies are corrected; recommending a decrease in funding to the site; and requiring specific training for site investigators or staff members.

## APPENDIX IX: PARTICIPANT APPLICATION INSTRUCTIONS AND DIARY FOR IMIQUIMOD (ZYCLARA)

### Instructions for Inserting Imiquimod 2.5% Cream

You have been randomized to receive topical Imiquimod cream once a day at night for 16 weeks. Please follow the directions below for the topical cream you have been given.

On weeks 1 and 2, you will apply one actuation (pump) daily and it will be divided as shown below; after two weeks this will be increased to two actuations, or one per side.

1. Imiquimod Pump

2. Apply one actuation (pump) to either right or left finger.

[figure not shown]
3. Divide this dose in half to one finger on the left and right hand.

4. Apply one finger inside the anus and spread the cream as far as you can reach from side to side. Repeat with opposite hand.

5. Alternatively, remove plunger from syringe and pump the cream into the top.

6. Insert left finger to the first joint and spread the cream evenly as far as you can reach; repeat on right side.

Repeat this once a day; at the two-week follow-up visit the clinician may instruct you to increase this to two actuations a day (one to each side). Inform the study staff of any severe side effects.

If instructed to also treat the outside (perianus) apply an additional actuation around the anal opening.

Record on the diary each application.

Inform the study staff of any severe side effects.

Store the bottle of Imiquimod upright at room temperature.

## PROTOCOL AMC-088 IMIQUIMOD PARTICIPANT DIARY

### 2.5% TOPICAL IMIQUIMOD FOR TREATMENT OF HIGH-GRADE ANAL SQUAMOUS INTRAEPITHELIAL LESIONS IN HIV-INFECTED MEN AND WOMEN

Only the recipient of the study treatment should complete this card. Study personnel may write on this card to document their interview and clarification of information recorded by the participant. However, all primary information should be the subject's; all entries by study personnel should be dated and initialed. Study personnel who annotate this record should sign the last page of this document and print their name clearly.

Study cycle: 2 weeks

Today's date: \_\_\_\_\_ / \_\_\_\_\_ / \_\_\_\_\_

Subject ID: \_\_\_\_\_ - \_\_\_\_\_ - \_\_\_\_\_

### **STUDY PARTICIPANTS MUST BRING THIS COMPLETED DIARY CARD AND ALL STUDY DRUG CONTAINERS TO EACH STUDY VISIT DURING TREATMENT ADMINISTRATION.**

Complete this card every day for the first 14 days of the study; day number 1 is \_\_\_\_\_ You will complete this card until ( \_\_\_\_\_ / \_\_\_\_\_ / \_\_\_\_\_ ) and return the card to the study site in person at your next visit.

You may receive a telephone call from the study nurse or coordinator to clarify information you have written. Feel free to write any concerns or questions in the boxes at the bottom of each page.

COORDINATORS: Distribute the applicable section(s) of the imiquimod diary(ies) at each treatment visit. Please ensure all pages of the diary are provided to the participant at each visit when the diary distributed. The diary(ies) **must** be collected at each visit.

Starting on your office visit day, please record the date and time of the application of medication and any reactions that occur at the treatment site. Estimate the severity of the following reactions AT THE APPLICATION SITE using the following definitions:

**Mild:** An awareness of symptoms, easily tolerated

**Moderate:** Discomfort is enough to interfere with your usual daily activities.

**Severe:** Incapacitating and you are unable to participate in activities that you usually do.

Week	Day 1	Day 2	Day 3	Day 4	Day 5	Day 6	Day 7
Date (MM/DD/YY)	____ / ____ / ____	____ / ____ / ____	____ / ____ / ____	____ / ____ / ____	____ / ____ / ____	____ / ____ / ____	____ / ____ / ____
Applied?	 Yes  1 pump  No  2 pumps	 Yes  1 pump  No  2 pumps	 Yes  1 pump  No  2 pumps	 Yes  1 pump  No  2 pumps	 Yes  1 pump  No  2 pumps	 Yes  1 pump  No  2 pumps	 Yes  1 pump  No  2 pumps
Pain or Tenderness	 None  Mild  Moderate  Severe	 None  Mild  Moderate  Severe	 None  Mild  Moderate  Severe	 None  Mild  Moderate  Severe	 None  Mild  Moderate  Severe	 None  Mild  Moderate  Severe	 None  Mild  Moderate  Severe
Bleeding	 None  Mild  Moderate  Severe	 None  Mild  Moderate  Severe	 None  Mild  Moderate  Severe	 None  Mild  Moderate  Severe	 None  Mild  Moderate  Severe	 None  Mild  Moderate  Severe	 None  Mild  Moderate  Severe
Other:	 None  Mild  Moderate  Severe	 None  Mild  Moderate  Severe	 None  Mild  Moderate  Severe	 None  Mild  Moderate  Severe	 None  Mild  Moderate  Severe	 None  Mild  Moderate  Severe	 None  Mild  Moderate  Severe
Other:	 None  Mild  Moderate  Severe	 None  Mild  Moderate  Severe	 None  Mild  Moderate  Severe	 None  Mild  Moderate  Severe	 None  Mild  Moderate  Severe	 None  Mild  Moderate  Severe	 None  Mild  Moderate  Severe
Comments							

Subject ID#: \_\_\_\_ - \_\_\_\_ - \_\_\_\_

Dates: \_\_\_\_ / \_\_\_\_ / \_\_\_\_ to \_\_\_\_ / \_\_\_\_ / \_\_\_\_

Starting on your office visit day, please record the date and time of the application of medication and any reactions that occur at the treatment site. Estimate the severity of the following reactions AT THE APPLICATION SITE using the following definitions:

**Mild:** An awareness of symptoms, easily tolerated

**Moderate:** Discomfort is enough to interfere with your usual daily activities.

**Severe:** Incapacitating and you are unable to participate in activities that you usually do.

Week 2	Day 8	Day 9	Day 10	Day 11	Day 12	Day 13	Day 14
Date (MM/DD/YY)	____ / ____ / ____	____ / ____ / ____	____ / ____ / ____	____ / ____ / ____	____ / ____ / ____	____ / ____ / ____	____ / ____ / ____
Applied?	 Yes  1 pump  No  2 pumps	 Yes  1 pump  No  2 pumps	 Yes  1 pump  No  2 pumps	 Yes  1 pump  No  2 pumps	 Yes  1 pump  No  2 pumps	 Yes  1 pump  No  2 pumps	 Yes  1 pump  No  2 pumps
Pain or Tenderness	 None  Mild  Moderate  Severe	 None  Mild  Moderate  Severe	 None  Mild  Moderate  Severe	 None  Mild  Moderate  Severe	 None  Mild  Moderate  Severe	 None  Mild  Moderate  Severe	 None  Mild  Moderate  Severe
Bleeding	 None  Mild  Moderate  Severe	 None  Mild  Moderate  Severe	 None  Mild  Moderate  Severe	 None  Mild  Moderate  Severe	 None  Mild  Moderate  Severe	 None  Mild  Moderate  Severe	 None  Mild  Moderate  Severe
Other:	 None  Mild  Moderate  Severe	 None  Mild  Moderate  Severe	 None  Mild  Moderate  Severe	 None  Mild  Moderate  Severe	 None  Mild  Moderate  Severe	 None  Mild  Moderate  Severe	 None  Mild  Moderate  Severe
Other:	 None  Mild  Moderate  Severe	 None  Mild  Moderate  Severe	 None  Mild  Moderate  Severe	 None  Mild  Moderate  Severe	 None  Mild  Moderate  Severe	 None  Mild  Moderate  Severe	 None  Mild  Moderate  Severe
Comments							

Other Complaints or Illnesses	Date (month/day/year)		Severity
	Started	Last Present	
			 Mild  Moderate  Severe
			 Mild  Moderate  Severe
			 Mild  Moderate  Severe
			 Mild  Moderate  Severe
			 Mild  Moderate  Severe
			 Mild  Moderate  Severe
			 Mild  Moderate  Severe

Comments or Concerns:

Subject ID#: \_\_\_\_ - \_\_\_\_ - \_\_\_\_

Dates: \_\_\_\_ / \_\_\_\_ / \_\_\_\_ to \_\_\_\_ / \_\_\_\_ / \_\_\_\_

**Please list any NEW prescription or over the counter medications or supplements that you took beginning on Day 1 and ending on Day 14 during this cycle. You do not have to list your HIV medications or any other drugs that you were taking regularly since the start of the study.**

Name of Medication	Date (mm/dd/yy)		Maximum Daily Dose	Reason for Medication
	Started	Last Taken		
If during the 14 days you did not take any medications check the box here:  None				

Comments or Concerns:

[figure not shown]
## APPENDIX X: PARTICIPANT APPLICATION INSTRUCTIONS AND DIARY FOR EFUDEX (5-FLUOROURACIL 5%)

### Instructions for Inserting 5-FU Cream

[figure not shown]
You have been randomized to receive topical 5-FU cream for 16 weeks. Please follow the directions below for the topical cream you have been given.

1. Open tube of 5-FU

[figure not shown]
2. Remove plunger from applicator.

[figure not shown]
3. Insert opening of tube into top of applicator and squeeze a small amount into applicator.

4. Re-insert the plunger until it reaches the .5ml mark on the applicator; any excess cream can be wiped off.

5. Find a comfortable position ex. squatting, lying on side, one leg raised, and insert the applicator into the anus approx.  $\frac{1}{2}$ ", then push the plunger until it stops.

6. Insert left finger to the first joint and spread the cream evenly as far as you can reach; repeat on right side.

7. Alternatively, place  $\frac{1}{2}$  the amount (or .25ml) on your left or right finger then follow instruction in #6.

8. Insert any remaining cream on the outside into the anus, then clean off any excess.

Repeat this procedure for 5 days, twice a day. Then stop for 9 days. Repeat this two week cycle for 16 weeks.

Inform the study staff if you have severe side effects.

## PROTOCOL AMC-088 5-FU PARTICIPANT DIARY

### 5% TOPICAL 5-FU FOR TREATMENT OF HIGH-GRADE ANAL SQUAMOUS INTRAEPITHELIAL LESIONS IN HIV-INFECTED MEN AND WOMEN

Only the recipient of the study treatment should complete this card. Study personnel may write on this card to document their interview and clarification of information recorded by the participant. However, all primary information should be the subject's; all entries by study personnel should be dated and initialed. Study personnel who annotate this record should sign the last page of this document and print their name clearly.

Study cycle: 2 weeks

Today's date: \_\_\_\_\_ / \_\_\_\_\_ / \_\_\_\_\_

Subject ID: \_\_\_\_\_ - \_\_\_\_\_ - \_\_\_\_\_

Doses you should apply: \_\_\_\_\_

#### STUDY PARTICIPANTS MUST BRING THIS COMPLETED DIARY CARD AND ALL STUDY DRUG CONTAINERS TO EACH STUDY VISIT DURING TREATMENT ADMINISTRATION.

Complete this card every day for the first 14 days of the study; day number 1 is \_\_\_\_\_ You will complete this card until (\_\_\_\_ / \_\_\_\_ / \_\_\_\_ ) and return the card to the study site in person at your next visit.

You may receive a telephone call from the study nurse or coordinator to clarify information you have written. Feel free to write any concerns or questions in the boxes at the bottom of each page.

COORDINATORS: Distribute the applicable section(s) of the imiquimod diaries at each treatment visit. Please ensure all pages of the diary are provided to the participant at each visit when the diary distributed. The diaries **must** be collected at each visit.

Starting on your office visit day, please record the date and time of the application of medication and any reactions that occur at the treatment site. Estimate the severity of the following reactions AT THE APPLICATION SITE using the following definitions:

**Mild:** An awareness of symptoms, easily tolerated

**Moderate:** Discomfort is enough to interfere with your usual daily activities.

**Severe:** Incapacitating and you are unable to participate in activities that you usually do.

Cycle ____ Week 1	Day 1		Day 2		Day 3		Day 4		Day 5		Day 6		Day 7	
Date (MM/DD/YY)	/	/	/	/	/	/	/	/	/	/	/	/	/	/
Applied?	AM	PM	Day Off			Day Off								
	 Yes	 Yes												
Pain or Tenderness	 None		 None		 None									
	 Mild		 Mild		 Mild		 Mild		 Mild		 Mild		 Mild	
Bleeding	 Moderate		 Moderate		 Moderate									
	 Severe		 Severe		 Severe		 Severe		 Severe		 Severe		 Severe	
Other:	 None		 None		 None									
	 Mild		 Mild		 Mild		 Mild		 Mild		 Mild		 Mild	
Other:	 None		 None		 None									

Subject ID#: \_\_\_\_ - \_\_\_\_ - \_\_\_\_

Dates: \_\_\_\_ / \_\_\_\_ / \_\_\_\_ to \_\_\_\_ / \_\_\_\_ / \_\_\_\_

	 Mild  Moderate  Severe						
Comments							

Subject ID#: \_\_\_\_ - \_\_\_\_ - \_\_\_\_

Dates: \_\_\_\_ / \_\_\_\_ / \_\_\_\_ to \_\_\_\_ / \_\_\_\_ / \_\_\_\_

Starting on your office visit day, please record the date and time of the application of medication and any reactions that occur at the treatment site. Estimate the severity of the following reactions AT THE APPLICATION SITE using the following definitions:

**Mild:** An awareness of symptoms, easily tolerated

**Moderate:** Discomfort is enough to interfere with your usual daily activities.

**Severe:** Incapacitating and you are unable to participate in activities that you usually do.

Cycle ____ Week 2	Day 8	Day 9	Day 10	Day 11	Day 12	Day 13	Day 14
Date (MM/DD/YY)	/ /	/ /	/ /	/ /	/ /	/ /	/ /
Applied?	Day Off						
Pain or Tenderness	 None						
	 Mild						
	 Moderate						
	 Severe						
Bleeding	 None						
	 Mild						
	 Moderate						
	 Severe						
Other:	 None						
	 Mild						
	 Moderate						
	 Severe						
Other:	 None						
	 Mild						
	 Moderate						

Subject ID#: \_\_\_\_ - \_\_\_\_ - \_\_\_\_

Dates: \_\_\_\_ / \_\_\_\_ / \_\_\_\_ to \_\_\_\_ / \_\_\_\_ / \_\_\_\_

	 Severe						
Comments							

Other Complaints or Illnesses	Date (month/day/year)		Severity
	Started	Last Present	
			 Mild  Moderate  Severe
			 Mild  Moderate  Severe
			 Mild  Moderate  Severe
			 Mild  Moderate  Severe
			 Mild  Moderate  Severe
			 Mild  Moderate  Severe
			 Mild  Moderate  Severe

Subject ID#: \_\_\_\_ - \_\_\_\_ - \_\_\_\_

Dates: \_\_\_\_ / \_\_\_\_ / \_\_\_\_ to \_\_\_\_ / \_\_\_\_ / \_\_\_\_

Comments or Concerns:

**Please list any NEW prescription or over the counter medications or supplements that you took beginning on Day 1 and ending on Day 14 during this cycle. You do not have to list your HIV medications or any other drugs that you were taking regularly since the start of the study.**

Name of Medication	Date (mm/dd/yy)		Maximum Daily Dose	Reason for Medication
	Started	Last Taken		

Subject ID#: \_\_\_\_ - \_\_\_\_ - \_\_\_\_

Dates: \_\_\_\_ / \_\_\_\_ / \_\_\_\_ to \_\_\_\_ / \_\_\_\_ / \_\_\_\_

If during the 14 days you did not take any medications check the box here:  None				

Comments or Concerns:

## APPENDIX XI: PROTOCOL AMC-088 SMOKING STATUS/ RECENT SEXUAL HISTORY QUESTIONNAIRE

Subject ID number: \_\_\_\_\_

Date completed: \_\_\_\_\_ Study Week number: \_\_\_\_\_

**NOTE TO STAFF:** Please answer question #1, then give to subject. It is preferable that the questionnaire be self-administered.

1. Was this questionnaire self-administered or interviewer-administered?

Self-administered

Interviewer administered

***Thank you for taking this questionnaire. This form will ask about cigarette smoking. It will also ask about sex you may have had in the last 6 months.***

2. How often do you currently smoke cigarettes? (Choose one)

Not at all (skip to question 4)

Some days

Every day

I prefer not to answer (skip to question 4)

3. On average over the past 6 months, how many cigarettes have you smoked per day? (1 pack equals 20 cigarettes)

\_\_\_\_\_

***The next few questions will ask about men or women you may have had sex with in the past 6 months. Let's review some words so that we agree on what we are talking about. By "having sex" we mean oral sex, anal sex, oral-anal sex, or vaginal sex.***

**ANAL SEX** is when a man puts his penis into someone's rectum, anus, or butt.

**ORAL SEX** is when someone puts his or her mouth or tongue to a woman's vagina or clitoris or on a man's penis.

**ORAL/ANAL SEX** is when someone puts his or her mouth or tongue to someone's anus (also known as rimming).

**VAGINAL SEX** is when a man puts his penis in a woman's vagina.

1. Have you ever had sex with a man (even only once)?

Yes

No (skip to question 8)

I prefer not to answer (skip to question 8)

2. Have you ever had sex by having a penis inserted into your anus (even only once)?

Yes

No

I prefer not to answer

3. Have you had sex of any kind with a man in the past 6 months?

Yes

No (skip to question 8)

I prefer not to answer (skip to question 8)

4. How many men have you had sex with in the past 6 months?

1

2 to 5

6 to 10

More than 10

5. With how many men have you had receptive anal sex with in the past 6 months (i.e. have sex by putting their penis into your anus)?

0 (skip to question 7)

1

2 to 5

6 to 10

More than 10

6. How often did your sex partner use a condom during receptive anal sex?

Every time (100%)

Mostly

Half the time

Occasionally

Never (0%)

7. In the past 6 months, how many men put their mouth or tongue on your anus?

0

1

2 to 5

6 to 10

More than 10

8. In the past 6 months, have you had sex with a woman?

Yes

No (skip to the end of the questionnaire)

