### **2.2 Secondary Objectives**

- To describe the efficacy of intra-anal imiquimod 2.5% for treatment of anal HSIL compared to observation only. Note: this objective is no longer powered to establish efficacy.
- To assess the safety and tolerability of intra-anal imiquimod 2.5% and topical 5FU.
- To compare the efficacy of intra-anal imiquimod 2.5% and topical 5FU.
- To assess for partial response of intra-anal imiquimod 2.5% or topical 5FU as compared to observation only.
- To evaluate the effect of intra-anal imiquimod 2.5% and topical 5-FU on HPV persistence.
- To evaluate anal HSIL outcomes at Week 44.
- To evaluate the effect of behavioral patterns including tobacco smoking and sexual activity on treatment efficacy, tolerability, and HPV.

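### In Appendix XI the smoking-item skip points to the male-partner count, so anyone following it literally bypasses three sexual-history items according to their smoking answer

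*Combined protocol and SAP*

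**What the plan says.** Appendix XI opens with item 1 (mode of administration) and item 2 (current smoking), and closes that block with item 3: "3. On average over the past 6 months, how many cigarettes have you smoked per day". Under item 2, two answers carry a skip: "Not at all (skip to question 4" and "I prefer not to answer (skip to question 4".

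After an introduction and some definitions, numbering starts again: "1. Have you ever had sex with a man (even only once", then "2. Have you ever had sex by having a penis inserted into your anus (even only once", then a third item on any sex with a man in the past 6 months. Item 4 of this block reads "How many men have you had sex with in the past 6 months". Its options run from 1 to more than 10, with neither a zero nor a decline option. Staff are told that self-administration is preferred.

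The form is used at Weeks 0, 20 and 44 and at early treatment discontinuation (sections 6.2.1, 6.6.1, 6.11.1 and 6.12; Appendix II). It serves a secondary objective in section 2.2: "To evaluate the effect of behavioral patterns including tobacco smoking and sexual activity on treatment efficacy, tolerability, and HPV". Section 10.8 plans regression models for this by treatment arm. It does not say which questionnaire items enter as covariates or how missing answers are handled.

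**The concern.** Items 1 and 3 of the sexual-history block are filter items: they send people without male partners on to item 8. A participant who obeys the smoking skip never meets them, nor item 2 on lifetime receptive anal sex. Whether those three items are answered would then depend on the answer about smoking. Smoking and sexual activity are the two exposures that the objective names, so missingness in one would be tied to the value of the other.

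A second effect follows. Someone sent straight to item 4 who has had no male partner in the past 6 months must leave it blank or choose a count of at least one that is untrue.

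**Working it through.** No sample size, power or alpha figure is involved. The check is a trace of the skip instructions.

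**Step 1: is the restart in numbering real, or produced by reading the PDF?** Compare the skip targets under the printed numbering (sexual-history items 1 to 9) and under continuous numbering (the same items as 4 to 12).

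| Instruction | Target if numbering restarts | Target if numbering is continuous |
|---|---|---|
| Skip to 8, from the items on ever and recent sex with a man | Sex with a woman: coherent | Number of receptive-sex partners: incoherent for someone with no male partner |
| Skip to 7, after zero receptive-sex partners | Men's oral-anal contact: coherent | Number of male partners: points backwards |
| Skip to 4, from the smoking item | Number of male partners: bypasses three items | Ever sex with a man: coherent |

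The later skips work only with the restart; the smoking skip works only without it. At least one instruction is wrong under either reading, so text extraction does not explain the conflict. The simplest account is that the smoking skip was left on a different numbering from the rest of the form.

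**Step 2: literal routing on the form as printed.**

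| Participant | Smoker | Non-smoker, or declines the smoking item |
|---|---|---|
| Male partner in past 6 months | Items 1, 2, 3, then 4 onward | Item 4 onward |
| Sex with a man in the past, none in 6 months | Items 1, 2, 3, then 8 onward | Item 4 (no valid answer), 5, 7, then 8 onward |
| Never sex with a man | Item 1, then 8 onward | Item 4 (no valid answer), 5, 7, then 8 onward |

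Item 6 (condom use) is reached only when item 5 is not zero, and item 9 only when item 8 is yes. Items 5 and 7 both offer zero, so only item 4 has no true answer for someone without a recent male partner.

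**Step 3: what can be recovered.**
- A valid answer to item 4 (at least 1) implies yes to items 1 and 3.
- An answer of at least 1 to item 5 implies yes to item 2.
- Zero at item 5 leaves item 2 unknown, because item 2 is a lifetime question.
- A blank at item 4 leaves items 1 and 3 unknown.
- An item 4 answer from someone who was never asked item 3 may be a forced count, so the first rule is weaker for such people.

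**Step 4: size.** Share of forms lacking items 1 to 3 = p × f, where p is the share of non-smokers and decliners and f is the share of those who obeyed the skip. The documents give neither. With f = 0 the share is 0; with f = 1 it is p.

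**Step 5: forms still to come.** Version 8.0 is dated 02AUG2023. Enrolment closed on 01JUL2023 after running at about one participant a month (section 10.1). All Week 0 forms were therefore due before version 8.0. On nominal visit dates:
- Week 20 forms were outstanding for people enrolled after 15 March 2023 (140 days earlier). That is 108 days to closure, or 108 / 30.4 ≈ 3.6, so about 3 to 4 participants.
- Week 44 forms were outstanding for people enrolled after 28 September 2022 (308 days earlier). That is 276 days, or 276 / 30.4 ≈ 9.1, so about 9 participants.

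Most forms already existed, so most of the benefit lies in the analysis rather than in the reprint.

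**The case against.** The intention is plain: non-smokers should skip the cigarettes-per-day item and carry on. The sexual-history introduction is printed directly after that item, and many people will simply read on. The form may be interviewer-administered, and data are entered through an electronic system with validation checks whose screens are not in the documents. It may route correctly. All of this stands, and it is why the amount of missing data cannot be stated.

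A reader might infer that sexual-history data are missing for non-smokers by design, or that joint models would lose most non-smokers. The documents support neither. Even under literal routing, non-smokers reach item 4 and what follows: partner count, receptive partners, condom use where relevant, oral-anal contact, and sex with women. Section 10.8 names no covariates, so nothing says that items 1 to 3 would enter a model, and part of their content can be recovered from items 4 and 5.

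A reader might also infer that item 4 lacks a zero option in its own right. It does not: item 4 is meant for people who answered yes to item 3, so starting at 1 is correct. The problem arises only because the skip goes round item 3.

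What the objection does not remove is the wrong instruction on a form meant mainly for self-completion, with no stated rule for noticing or handling its effect.

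**Conclusion.** The smoking skip in Appendix XI is wrong as printed. Followed literally, it makes sexual-history items 1 to 3 missing for non-smokers and for those who decline the smoking item, and leaves some of them with no valid answer at item 4. That conclusion rests on the text of the form alone.

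The practical size is unknown. It depends on how many participants obeyed the instruction and on how the electronic form was built. The consequence is confined to the secondary behavioural objective and its section 10.8 models; the primary endpoint does not use these data. This is a minor point, worth acting on because the check is simple and an unnoticed link between smoking and missing sexual history could mislead the behavioural analysis.

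**What to change.** 1. For any remaining visits and any reuse of the form, point both smoking skips to the first sexual-history item ("Have you ever had sex with a man (even only once"). No zero option is needed at item 4 once item 3 again filters who reaches it.
2. Before fitting the section 10.8 behavioural models, tabulate completion of sexual-history items 1 to 3 by response to the current-smoking item, at each visit. If completion does not differ by smoking response, nothing further is needed.
3. If the skip was followed, add a short rule to section 10.8. Bypassed items are missing and are not coded as negative. Items 1 and 3 are recovered as yes from a valid item 4 answer, and item 2 as yes from an item 5 answer of at least 1. Item 4 answers from people who were not asked item 3 are treated with caution. Items 1 to 3 and smoking are not placed together in one complete-case model.

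The cost is one corrected skip target, one data listing and, only if the listing shows a problem, a brief addition to the analysis text.
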